- There may be situations in which an SAE has occurred and the investigator has minimal information to include in the initial report to GSK. However, **it is very important that the investigator always make an assessment of causality for every event before the initial transmission of the SAE data to GSK.**
- The investigator may change his/her opinion of causality in light of follow-up information and send an SAE follow-up report with the updated causality assessment.
- The causality assessment is one of the criteria used when determining regulatory reporting requirements.

Follow-up of AE and SAE

- The investigator is obligated to perform or arrange for the conduct of supplemental measurements and/or evaluations as medically indicated or as requested by GSK to elucidate the nature and/or causality of the AE or SAE as fully as possible. This may include additional laboratory tests or investigations, histopathological examinations, or consultation with other health care professionals.
- If a participant dies during participation in the study or during a recognized follow-up period, the investigator will provide GSK with a copy of any post-mortem findings including histopathology.
- New or updated information will be recorded in the originally completed CRF.
- The investigator will submit any updated SAE data to t GSK within 24 hours of receipt of the information.

Reporting of SAE to GSK

SAE Reporting to GSK via Electronic Data Collection Tool

- The primary mechanism for reporting SAE to GSK will be the electronic data collection tool.
- If the electronic system is unavailable, then the site will use the paper SAE data collection tool (see next section) to ensure sending the data to GSK within 24 hours following knowledge of the SAE.
- The investigator or medically-qualified sub-investigator must show evidence within the eCRF (e.g., check review box, signature, etc.) of review and verification of the relationship of each SAE to study treatment/study participation (causality) within 72 hours of SAE entry into the eCRF.
- The site will enter the SAE data into the electronic system as soon as it becomes available.
- After the study is completed at a given site, the electronic data collection tool will be taken off-line to prevent the entry of new data or changes to existing data.
- If a site receives a report of a new SAE from a study participant or receives updated data on a previously reported SAE after the electronic data collection tool has been taken off-line, then the site can report this information on a paper SAE form (see next section) or to the GSK Medical Monitor by telephone.
- Contacts for SAE reporting can be found in SRM.

SAE Reporting to GSK via Paper CRF

- Facsimile transmission of the SAE paper CRF is the preferred method to transmit this information to the **GSK Medical Monitor**.
- In rare circumstances and in the absence of facsimile equipment, notification by telephone is acceptable with a copy of the SAE data collection tool sent by overnight mail or courier service.
- Initial notification via telephone does not replace the need for the investigator to complete and sign the SAE CRF pages within the designated reporting time frames.
- Contacts for SAE reporting can be found in SRM.

12.5. Appendix 5: Contraceptive Guidance and Collection of Pregnancy Information

Definitions

Woman of Childbearing Potential (WOCBP)

A woman is considered fertile following menarche and until becoming post-menopausal unless permanently sterile (see below)

Women in the following categories are not considered WOCBP

1. Premenarchal
2. Premenopausal female with ONE of the following:
 - Documented hysterectomy
 - Documented bilateral salpingectomy
 - Documented bilateral oophorectomy

Note: Documentation can come from the site personnel's: review of participant's medical records, medical examination, or medical history interview.

3. Postmenopausal female
 - A postmenopausal state is defined as no menses for 12 months without an alternative medical cause. A high follicle stimulating hormone (FSH) level in the postmenopausal range may be used to confirm a postmenopausal state in women not using hormonal contraception or hormonal replacement therapy (HRT). However, in the absence of 12 months of amenorrhea, a single FSH measurement is insufficient.
 - Females on HRT and whose menopausal status is in doubt will be required to use one of the non-hormonal highly effective contraception methods if they wish to continue their HRT during the study. Otherwise, they must discontinue HRT to allow confirmation of postmenopausal status before study enrollment.

Contraception Guidance

Female participants

Female participants of childbearing potential are eligible to participate if they agree to use a highly effective method of contraception consistently and correctly as described in [Table 3](#).

Table 3 Highly Effective Contraceptive Methods

Highly Effective Contraceptive Methods That Are User Dependent^a Failure rate of <1% per year when used consistently and correctly.

Combined (estrogen- and progestogen-containing) hormonal contraception associated with inhibition of ovulation^b
 
 • oral • intravaginal • transdermal

Progestogen-only hormonal contraception associated with inhibition of ovulation^b
 
 • injectable

Highly Effective Methods That Are User Independent

 • Implantable progestogen-only hormonal contraception associated with inhibition of ovulation^b • Intrauterine device (IUD) • Intrauterine hormone-releasing system (IUS) • bilateral tubal occlusion

Vasectomized partner
 
(A vasectomized partner is a highly effective contraception method provided that the partner is the sole male sexual partner of the WOCBP and the absence of sperm has been confirmed. If not, an additional highly effective method of contraception should be used.)

Sexual abstinence
 
(Sexual abstinence is considered a highly effective method only if defined as refraining from heterosexual intercourse during the entire period of risk associated with the study drug. The reliability of sexual abstinence needs to be evaluated in relation to the duration of the study and the preferred and usual lifestyle of the participant.)

NOTES:

- a. Typical use failure rates may differ from those when used consistently and correctly. Use should be consistent with local regulations regarding the use of contraceptive methods for participants in clinical studies.
- b. Hormonal contraception may be susceptible to interaction with the study drug, which may reduce the efficacy of the contraceptive method. In this case two highly effective methods of contraception should be utilized at least 30 days prior to the first dose of study treatment and until 16 weeks after the last dose of mepolizumab

Pregnancy Testing

- WOCBP should only be included after a confirmed menstrual period and a negative highly sensitive urine (or serum, if locally required) pregnancy test
- Additional pregnancy testing should be performed at monthly intervals during the treatment period and at 4 weeks after the last dose of study treatment and as required locally.

- Pregnancy testing will be performed whenever a menstrual cycle is missed or when pregnancy is otherwise suspected.
- Pregnancy testing, with a sensitivity of 25 mIU/mL will be performed and assayed in a certified laboratory OR and assayed in the central laboratory OR using the test kit provided by the central laboratory / provided by the sponsor /approved by the sponsor and in accordance with instructions provided in its package insert.

Collection of Pregnancy Information

Female Participants who become pregnant

- Investigator will collect pregnancy information on any female participant, who becomes pregnant while participating in this study.
- Information will be recorded on the appropriate form and submitted to GSK within 24 hours of learning of a participant's pregnancy.
- Participant will be followed to determine the outcome of the pregnancy. The investigator will collect follow up information on participant and neonate, which will be forwarded to GSK Generally, follow-up will not be required for longer than 6 to 8 weeks beyond the estimated delivery date.
- Any termination of pregnancy will be reported, regardless of fetal status (presence or absence of anomalies) or indication for procedure.
- While pregnancy itself is not considered to be an AE or SAE, any pregnancy complication or elective termination of a pregnancy will be reported as an AE or SAE.
- A spontaneous abortion is always considered to be an SAE and will be reported as such.
- Any SAE occurring as a result of a post-study pregnancy which is considered reasonably related to the study treatment by the investigator, will be reported to GSK as described in [Appendix 4](#). While the investigator is not obligated to actively seek this information in former study participants, he or she may learn of an SAE through spontaneous reporting.

Any female participant who becomes pregnant while participating will discontinue mepolizumab.

12.6. Appendix 6: Liver Safety: Required Actions and Follow-up Assessments

Liver chemistry stopping and increased monitoring criteria have been designed to assure participant safety and evaluate liver event etiology.

Liver chemistry stopping criteria

Liver Chemistry Stopping Criteria – Liver Stopping Event	
ALT-absolute	Both ALT \geq 8xULN and \geq 2X baseline value
ALT Increase	Both ALT \geq 3xULN and \geq 1.5x baseline value that persists for \geq 4 weeks
Bilirubin^{1,2}	ALT \geq 3xULN and bilirubin \geq 2xULN (>35% direct bilirubin)
INR²	ALT \geq 3xULN and INR>1.5, if INR measured
Cannot Monitor	Both ALT \geq 3xULN and \geq 1.5x baseline value and cannot be monitored weekly for \geq 4 weeks
Symptomatic³	Both ALT \geq 3xULN and \geq 1.5x baseline value associated with symptoms (new or worsening) believed to be related to liver injury or hypersensitivity
Required Actions and Follow up Assessments following ANY Liver Stopping Event	
Actions	Follow Up Assessments

 Immediately discontinue study treatment. Report the event to GSK within 24 hours. Complete the liver event CRF and complete an SAE data collection tool if the event also meets the criteria for an SAE². Perform liver event follow up assessments. Monitor the participant until liver chemistries resolve, stabilize, or return to within baseline (laboratory assessments performed closest and prior to first dose of study treatment). Do not restart/rechallenge participant with study treatment. If restart/rechallenge not allowed, permanently discontinue study treatment and may continue participant in the study for any protocol-specified follow up assessments. 	
 Viral hepatitis serology⁴ Obtain INR and recheck with each liver chemistry assessment until the transaminases values show downward trend. Only in those with underlying chronic Hepatitis B at study entry (identified by positive Hepatitis B surface antigen) quantitative Hepatitis B DNA and Hepatitis delta antibody⁵. Obtain blood sample for pharmacokinetic (PK) analysis, within 1 week of the liver event⁶. Serum creatine phosphokinase (CPK) and lactate dehydrogenase (LDH). Fractionate bilirubin, if total bilirubin\geq2xULN Obtain complete blood count with differential to assess eosinophilia. Note: the mechanism of action of mepolizumab is lowering the eosinophils. Record the appearance or worsening of clinical symptoms of liver injury, or


MONITORING:
 
For bilirubin or INR criteria:
 
 Repeat liver chemistries (include ALT, AST, alkaline phosphatase, bilirubin) and perform liver event follow up assessments within 24 hrs. Monitor participants twice weekly until liver chemistries resolve, stabilize or return to within baseline. A specialist or hepatology consultation is recommended. 
For All other criteria:
 
 Repeat liver chemistries (include ALT, AST, alkaline phosphatase, bilirubin) and perform liver event follow up assessments within 24-72 hrs. Monitor participants weekly until liver chemistries resolve, stabilize or return to within baseline. 	
hypersensitivity, on the AE report form
 
 Record use of concomitant medications on the concomitant medications report form including acetaminophen, herbal remedies, other over the counter medications. Record alcohol use on the liver event alcohol intake case report form (CRF) page 
For bilirubin or INR criteria:
 
 Anti-nuclear antibody, anti-smooth muscle antibody, Type 1 anti-liver kidney microsomal antibodies, and quantitative total immunoglobulin G (IgG) or gamma globulins. Serum acetaminophen adduct high performance liquid chromatography (HPLC) assay (quantifies potential acetaminophen contribution to liver injury in participants with definite or likely acetaminophen use in the preceding week [James, 2009]). Liver imaging (ultrasound, magnetic resonance, or computerised tomography) and /or liver biopsy to evaluate liver disease: complete Liver Imaging and/or Liver Biopsy CRF forms.
--	--

- Serum bilirubin fractionation should be performed if testing is available. If serum bilirubin fractionation is not immediately available, discontinue study treatment for that participant if ALT \geq 3xULN **and** bilirubin \geq 2xULN. Additionally, if serum bilirubin fractionation testing is unavailable, **record presence of detectable urinary bilirubin on dipstick**, indicating direct bilirubin elevations and suggesting liver injury.
- All events of ALT \geq 3xULN **and** bilirubin \geq 2xULN (>35% direct bilirubin) or ALT \geq 3xULN **and** INR>1.5, if INR measured which may indicate severe liver injury (possible 'Hy's Law'), **must be reported as an SAE (excluding studies of hepatic impairment or cirrhosis)**; INR measurement is not required and the threshold value stated will not apply to participants receiving anticoagulants
- New or worsening symptoms believed to be related to liver injury (such as fatigue, nausea, vomiting, right upper quadrant pain or tenderness, or jaundice) or believed to be related to hypersensitivity (such as fever, rash or eosinophilia)
- Includes: Hepatitis A IgM antibody; Hepatitis B surface antigen and Hepatitis B Core Antibody (IgM); Hepatitis C RNA; Cytomegalovirus IgM antibody; Epstein-Barr viral capsid antigen IgM antibody (or if unavailable, obtain heterophile antibody or monospot testing); Hepatitis E IgM antibody
- If hepatitis delta antibody assay cannot be performed, it can be replaced with a PCR of hepatitis D RNA virus (where needed) [Le Gal, 2005].
- PK sample may not be required for participants known to be receiving placebo or non-GSK comparator treatments.) Record the date/time of the PK blood sample draw and the date/time of the last dose of study treatment prior to blood sample draw on the CRF. If the date or time of the last dose is unclear, provide the participant's best approximation. If the date/time of the last dose cannot be approximated OR a PK sample cannot be collected in the time period indicated above, do not obtain a PK sample. Instructions for sample handling and shipping are in the SRM.

Phase III-IV liver chemistry increased monitoring criteria with continued therapy

Liver Chemistry Increased Monitoring Criteria – Liver Monitoring Event	
Criteria	Actions
ALT $\geq 3 \times$ ULN and $\geq 1.5 \times$ baseline value but ALT $< 8 \times$ ULN and $< 2 \times$ baseline value and bilirubin $< 2 \times$ ULN without symptoms believed to be related to liver injury or hypersensitivity, and who can be monitored weekly for 4 weeks.	
 • Notify the GSK medical monitor within 24 hours of learning of the abnormality to discuss participant safety. • Participant can continue study treatment. • Participant must return weekly for repeat liver chemistries (ALT, AST, alkaline phosphatase, bilirubin) until they resolve, stabilise or return to within baseline • If at any time participant meets the liver chemistry stopping criteria, proceed as described above. • If, after 4 weeks of monitoring, ALT $< 3 \times$ULN and bilirubin $< 2 \times$ULN, monitor participants twice monthly until liver chemistries normalize or return to within baseline.

References

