8.1.1. Liver Chemistry Stopping Criteria

Liver chemistry stopping and increased monitoring criteria have been designed to assure participant safety and evaluate liver event etiology (in alignment with the FDA premarketing clinical liver safety guidance). These protocol guidelines are in alignment with FDA premarketing clinical liver safety guidance:

<http://www.fda.gov/downloads/Drugs/GuidanceComplianceRegulatoryInformation/Guidances/UCM174090.pdf>.

Figure 2 Liver Stopping and Monitoring Event Algorithm

Refer to Section 12.6 for Liver Safety Required Actions and Follow-up Assessments.

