9.4.4. Clinical Safety Laboratory Assessments

- Refer to Section 12.2 for the list of clinical laboratory tests to be performed and to the SoA for the timing and frequency.
- The investigator must review the laboratory report, document this review, and record any clinically relevant changes occurring during the study in the AE section of the CRF. The laboratory reports must be filed with the source documents. Clinically significant abnormal laboratory findings are those which are not associated with the underlying disease, unless judged by the investigator to be more severe than expected for the participant's condition.
- All laboratory tests with values considered clinically significantly abnormal during participation in the study or within 4 weeks after the last dose of study treatment should be repeated until the values return to normal or baseline or are no longer considered significantly abnormal by the investigator or GSK Medical Monitor.
- If such values do not return to normal/baseline within a period of time judged reasonable by the investigator, the etiology should be identified and the sponsor notified.
- All protocol-required laboratory assessments, as defined in Appendix 2, must be conducted in accordance with the laboratory manual and the SoA.
- If laboratory values from non-protocol specified laboratory assessments performed at the institution's local laboratory require a change in participant management or are considered clinically significant by the investigator (e.g., SAE or AE or dose modification), then the results must be recorded in the CRF.

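### The liver monitoring row in Protocol Section 12.6 cannot be met by anyone whose baseline ALT is 1.5×ULN or lower

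*Protocol*

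**What the plan says.** Protocol Section 12.6 has two liver tables.

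**Stopping.** The ALT-absolute row reads "Both ALT \geq 8xULN and \geq 2X baseline value". Two further ALT rows apply at lower values: "Both ALT \geq 3xULN and \geq 1.5x baseline value that persists for \geq 4 weeks" and "Both ALT \geq 3xULN and \geq 1.5x baseline value and cannot be monitored weekly for \geq 4 weeks". The remaining rows need ALT ≥3×ULN together with raised bilirubin (more than 35% direct), INR above 1.5, or symptoms; the symptom row also needs ≥1.5× baseline. Any stopping event must be reported to the sponsor within 24 hours.

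**Increased monitoring with treatment continued.** The row requires ALT ≥3×ULN and ≥1.5× baseline, "but ALT $< 8 \times$ ULN and $< 2 \times$ baseline value". It also requires bilirubin below 2×ULN, no relevant symptoms, and that weekly monitoring for 4 weeks is possible. Two of its actions are "Notify the GSK medical monitor within 24 hours of learning of the abnormality to discuss participant safety" and "Participant must return weekly for repeat liver chemistries".

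Section 8.1.1 presents the criteria as Figure 2, the "Liver Stopping and Monitoring Event Algorithm", and sends the reader to Section 12.6 for the required actions. Figure 2 is not visible in the text available.

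**The concern.** The monitoring row should cover whatever the ALT-absolute stopping row leaves over. The opposite of *both A and B* is *not A, or not B*. The row instead says *not A, and not B*, which is narrower.

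The literal result runs against the risk:

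- At baseline 2×ULN, an ALT of 3.9×ULN is a monitoring event, but 7.9×ULN, almost four times baseline, is not.
- At baseline 0.8×ULN, an ALT of 5×ULN, more than six times baseline, is not a monitoring event.
- A participant who cannot attend weekly is stopped and reported within 24 hours. The same participant, if able to attend weekly, has no mandated action when the rise is first seen.

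Two explicit actions are at stake: the 24-hour notification and the weekly chemistries. The stopping rule for a rise lasting at least 4 weeks also depends on repeat tests, and this row is what should order them.

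**Working it through.** **Inputs.** The thresholds come from the two Section 12.6 tables. The visit spacing (every 4 weeks, ±1 week) comes from the Schedule of Activities in Section 2. The plan states no figure to reproduce.

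**Notation.** Let a = ALT/ULN and b = baseline ALT/ULN. Assume no symptoms, bilirubin <2×ULN, INR ≤1.5 or not measured, weekly monitoring possible, and a rise not yet present for 4 weeks.

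- ALT-absolute stopping: a ≥ 8 and a ≥ 2b.
- Monitoring as written: a ≥ 3, a ≥ 1.5b, a < 8 and a < 2b, so max(3, 1.5b) ≤ a < min(8, 2b).

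**When the monitoring row is empty.** It needs 3 ≤ a < 2b, hence b > 1.5. If b ≤ 1.5 then 2b ≤ 3 and no value qualifies. It is also empty when 1.5b ≥ 8, that is, b ≥ 5.33.

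**What falls in neither row.** Among values with a ≥ 3 and a ≥ 1.5b, the gap is max(3, 2b) ≤ a < 8 for b below 4, nothing at b = 4, and max(8, 1.5b) ≤ a < 2b for b above 4. A grid of ALT values in steps of 0.01×ULN agrees.

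| Baseline (×ULN) | Monitoring row covers (×ULN) | In neither row (×ULN) | Share of the range below 8×ULN that is monitored |
|---|---|---|---|
| 0.5, 0.8, 1.0, 1.5 | nothing | 3 to <8 | 0/5 = 0% |
| 1.6 | 3 to <3.2 | 3.2 to <8 | 0.2/5 = 4% |
| 2 | 3 to <4 | 4 to <8 | 1/5 = 20% |
| 2.5 | 3.75 to <5 | 5 to <8 | 1.25/4.25 = 29% |
| 3 | 4.5 to <6 | 6 to <8 | 1.5/3.5 = 43% |
| 4 | 6 to <8 | none | 2/2 = 100% |
| 5 | 7.5 to <8 | 8 to <10 | 0.5/0.5 = 100% |

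The last column compares interval lengths. It is not a proportion of participants. Values below 1.5× baseline lie outside the monitoring row and the ALT-only stopping rows by design and are not counted as gaps.

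**Timing from scheduled draws alone.** Consecutive visits are 28 days apart, each with an offset of −7 to +7 days.

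- The next draw comes 28 − 14 = 14 to 28 + 14 = 42 days after the finding.
- If that interval is at least 28 days, 4-week persistence can be confirmed then, at 28 to 42 days.
- If it is shorter (105 of the 225 offset pairs, unweighted), the following visit is needed. An interval below 28 days requires the second visit's offset to be smaller than the first's, so the first offset is at least −6. The latest confirmation is 56 + 7 + 6 = 69 days.
- For a rise first seen at Visits 2 to 4, confirmation therefore falls 28 to 69 days later.

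**Check of the correction.** Define monitoring as a ≥ 3, a ≥ 1.5b and not (a ≥ 8 and a ≥ 2b). Any value meeting ALT-absolute stopping already has a ≥ 3 and a ≥ 1.5b, so every value in range falls in exactly one row. The grid gives 0 uncovered and 0 doubly covered points at every tested baseline from 0.5 to 6×ULN.

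**The case against.** The algebra is not in dispute. The case against concerns how much it matters.

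- *Figure 2 may show the correct branch.* It may. But Section 8.1.1 sends sites to Section 12.6 for the actions, so a correct figure would leave two differing rules and the row would still need correcting.
- *Other safeguards exist.* Section 9 tells sites to raise immediate safety concerns with the sponsor at once. Section 9.4.4 says clinically significant abnormal values "should be repeated until the values return to normal or baseline". Section 12.2 allows extra tests. All three rest on the investigator's judgement, and none sets a weekly interval or a 24-hour limit.
- *The intent is visible.* The row for participants who cannot be monitored implies a choice between weekly monitoring and stopping, and many sites will read it that way. This is fair, and it makes a drafting slip the likely explanation. A safety trigger should still not depend on the reader repairing its logic.
- *The delays are worst cases.* They assume nobody acts between visits, and the upper ends need near-opposite visit offsets. This stands; they are bounds, not expectations.
- *The correction leaves another hole.* With ALT 5×ULN, baseline 1×ULN and bilirubin ≥2×ULN that is at most 35% direct, an asymptomatic participant still meets neither the reworded row nor the bilirubin or ALT-absolute row. Section 6.2 admits Gilbert's syndrome, so such a case could arise. This is a separate gap already in the text, which the rewording neither creates nor closes.

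**Conclusion.** The concern holds, and the row is wrong as written. Read literally, it is void for every participant with baseline ALT at or below 1.5×ULN, which includes everyone with a normal baseline. It is only partly effective for baselines above 1.5 and below 4×ULN. The uncovered range at normal baseline is 3 to <8×ULN, under the conditions listed in the working. If any of those conditions fails through symptoms, directly raised bilirubin, high INR, inability to attend weekly or 4-week persistence, a stopping row applies.

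This is a gap in coverage and not a contradiction, since no value falls in both rows. The logic is exact. How many participants it could affect cannot be estimated without a baseline ALT distribution. The conclusion is limited to the Section 12.6 text. In a study whose primary objective is safety, a mandated liver trigger that does not fire for normal baselines needs correcting.

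**What to change.** In the monitoring row, replace the two upper ALT limits with: *but NOT (ALT ≥8×ULN and ≥2× baseline)*. Leave the lower limits and the bilirubin, symptom and weekly-attendance conditions as they are. Keeping the 1.5× baseline floor matters because Section 6.2 admits stable chronic liver disease.

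The sponsor's liver-safety function should confirm the wording, check that Figure 2 agrees, and notify sites. If SAP Table 2.51 (Section 13.8.5) is derived from these criteria, which the SAP does not say, its programming should use the corrected row. The indirect-bilirubin case can be considered at the same time.

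The cost is one reworded table row, carried in an amendment or a letter to sites, plus the figure check. It adds no visits or procedures beyond the weekly monitoring the row already describes.
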